#### 3.6.1 Providers

Provider assessments are completed after TranS-C training, at mid-treatment, and at post-treatment. See Figure 4 for provider timeline.

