#### 3.6.2 Patients

Patient assessments in the immediate TranS-C treatment conditions are completed at pre-treatment, mid-treatment, post-treatment, and six months after treatment (6FU). Patient assessments in the UC-DT

condition are completed at pre-treatment and four or eight weeks after pre-treatment (i.e., post UC-DT), depending on whether their county has been randomized to Adapted or Standard TranS-C, respectively. After the post UC-DT assessment, patients start delayed treatment with TranS-C. They subsequently complete assessments at mid-treatment, post-treatment, and 6FU. Note that patients do not complete a 6FU assessment after the delayed portion of UC-DT. This was a compromise made with CMCH partners, so that patients would not need to wait 7-8 months to receive treatment. See Figure 2 for patient timeline.

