## 4 PLANNED ANALYSES

### 4.1 Preliminary Analyses and Missing Data

Analyses will use all available data (intent-to-treat) [93]. If dropout is related to other variables, they will be included as predictors. Baseline between-group differences on demographic variables will be examined. These tests will not be used to select covariates in the primary intention-to-treat analysis [94-97]. Instead, covariates will be carefully selected at the conclusion of the trial—given the variations due to COVID-19 and the CMHC context (see Discussion)—and the potential influences of baseline differences will be evaluated as moderators (approach to moderation described below). Analyses comparing TranS-C to UC-DT will evaluate change in outcomes from pre-treatment to post-treatment. Analyses comparing Adapted to Standard TranS-C will evaluate change in outcomes from pre-treatment to post-treatment and pre-treatment to 6FU (see Method and Discussion for more details).

Distributions will be evaluated to detect outliers, and we will ensure that assumptions of planned analyses are met. Covariates will include the patient variables for which we stratified (i.e., age and presence of psychosis or substance use). For all statistical models, counties will be entered as dummy variables rather than a level of analysis due to the relatively small number of clusters. The average intraclass correlation on provider and patient level outcomes will be reported. The Benjamini–Hochberg procedure [98] will be used to correct for multiple testing for confirmatory analyses on the primary outcomes (i.e., sleep disturbance and acceptability) [99].

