### 4.3 Aim 1: Effectiveness Outcomes of Standard or Adapted TranS-C versus UC-DT

Multilevel modeling (MLM) [100-102] will be used to account for multiple observations nested within

patient. The level 1 equation will include dummy-coded time indicators as the predictor (0 = pretreatment, 1 = post-treatment). The level 2 equation will include dummy-coded treatment condition (0 = UC-DT, 1 = Adapted or Standard TranS-C), treatment by time interaction terms, and dummy-coded counties (0 = Alameda, 1 = Contra Costa, 2 = Kings, 3 = Monterey, 4 = Placer, 5 = Santa Cruz, 6 = Solano, 7 = Santa Clara, 8 = Santa Barbara, and 9 = Lake) as predictors. The treatment effects of interest will be significant treatment by time interactions at the 5% level on the primary outcome of sleep disturbance and the secondary outcomes of sleep-related impairment, functional impairment, and psychiatric symptoms, all modeled as continuous variables. Significant treatment by time interactions indicate that change in patient outcomes is significantly different comparing Adapted or Standard TranS-C to UC-DT. Significant interactions will be interpreted using planned contrasts (i.e., treatment effects on change from pre-treatment to post-treatment) and graphs. Additionally, the indirect effects of TranS-C relative to UC-DT on functional impairment and psychiatric symptoms through improvements in sleep disturbance and sleep-related impairment will be tested using multilevel structural equation modeling [103].

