#### **4.4 Aim 2: Adapted TranS-C versus Standard TranS-C on Fit to CMHC Context**

MLM will be used to account for multiple observations nested within providers. TranS-C treatment condition (Adapted versus Standard TranS-C) will be evaluated as a predictor of fit, operationalized as provider ratings of acceptability, feasibility, and appropriateness. The level 1 equation will include dummy-coded time indicators as the predictor (0 = pre-treatment, 1 = post-treatment). The level 2 equation will include dummy-coded treatment condition (0 = Standard TranS-C, 1 = Adapted TranS-C), treatment by time interaction terms, and dummy-coded counties (0 = Alameda, 1 = Contra Costa, 2 = Kings, 3 = Monterey, 4 = Placer, 5 = Santa Cruz, 6 = Solano, 7 = Santa Clara, 8 = Santa Barbara, and 9 = Lake) as predictors. The treatment effects of interest will be significant treatment by time interactions at the 5% level on the primary outcome of acceptability and the secondary outcomes of feasibility and appropriateness, all modeled as continuous variables. Significant treatment by time interactions indicate that change in perceptions of fit is significantly different comparing Adapted to Standard TranS-C. Significant interactions will be interpreted using planned contrasts (i.e., treatment effects on change from pre-treatment to post-treatment) and graphs.

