#### **4.6 Sensitivity Analyses**

Three sets of sensitivity analyses will be run to help account for the complexities of the COVID-19 pandemic and the CMHC context. In the first set, the analyses for Aims 1-3 will be conducted with (a) treatment completers, (b) patients who completed more than half the number of the suggested sessions (i.e., > 2 sessions for Adapted and > 4 sessions for Standard), and (c) patients who completed half or fewer of suggested sessions. In other words, these analyses will test the effectiveness of TranS-C at varying doses, which may be important considering evidence on “early responders” [104] and “real world” contexts where turnover and dropout can be high [105, 106]. In the second set of sensitivity analyses, we will assess whether any patients who did not complete post-treatment or 6FU had achieved meaningful clinical improvement by mid-treatment, using a reliable change index for the primary

outcome of PROMIS-SD [107]. For the sensitivity analyses, we will define these patients as completers, and we will use their mid-treatment assessment in place of a post-treatment assessment. Then, all pre- to post-treatment analyses for Aims 1-3 will be rerun. In the third set of sensitivity analyses, we will run the analyses for Aims 1-3 but only include post-treatment and 6FU assessments that were collected within 3 months of the target assessment date (e.g., a 6FU assessment that was completed nine months after treatment ended).

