First, we did not collect data from leadership at our partner CMHCs. The primary reason was that these leaders have many demands on their time and already had generously collaborated with us on the design and implementation of the study. However, we recognize that leadership-level factors can meaningfully impact implementation outcomes [109]. Thus, exploring leadership perspectives on TranS-C will be an important direction for future research. Second, we considered additional assessment methods for sleep and circadian problems, such as a diagnostic interview (e.g., the Duke Structured Interview for Sleep Disorders; [63]) and polysomnography. However, even without these more intensive diagnostic tools, some patients reported difficulty with the length of assessments. Additionally, we were interested in recruiting patients with a broad range of symptom severity, which may have more ecological validity than a more restricted sample. That said, we acknowledge that there are certain outcomes that we will not be able to address due to this design choice (e.g., change in diagnostic status). Third, assessors are not blind to treatment condition at pre-treatment. To minimize burden on participants (e.g., reduce number of calls from team), assessors are in charge of the consent process, and therefore, they need to provide study-related information—such as number of assessments and treatment sessions—to the patients. At post-treatment and 6FU, we endeavor to keep the assessors blind but, as is common in clinical trials, there are ways that assessors may be able to infer treatment condition (e.g., slightly different assessment batteries). In rare instances, patients in the UC-DT condition ask assessors questions such as “when does treatment start?” or “when will I receive the workbook?” during the post-delay assessment. In such instances, the assessor may be able to ascertain that the patient has been assigned to the UC-DT condition. Assessors receive ongoing supervision and are thoroughly trained to deliver the surveys with integrity and minimal bias. Additionally, relative to interviews or clinical rating scales, the standardized surveys delivered by assessors are likely less vulnerable to bias (see Measures above). However, it is possible that assessor knowledge or hunches about patients’ condition may influence patient responses. Fourth, in the UC-DT condition, patients did not complete a 6FU assessment after the delay. This was a compromise made with CMCH partners, so that patients would not need to wait 7 to 8 months to receive treatment. Thus, analyses comparing TranS-C with UC-DT will evaluate outcomes from pre- to post-treatment, whereas analyses comparing Adapted versus Standard TranS-C can evaluate outcomes from pre- to post-treatment *and* pre- to 6FU. Depending on the outcomes from the trial, an important direction for future research will be testing the long-term effects of TranS-C relative to a control (e.g., UC-DT). Fifth, unforeseen challenges arose related to the COVID-19 pandemic and subsequent mandates in California (e.g., shelter-in-place). For some patients, sleep and circadian treatment became secondary to coping with other mental health ramifications of the pandemic (e.g., anxiety, isolation, grief) or even meeting basic needs of secure access to food and shelter [110]. Additionally, providers suddenly had more demands on their time, such as navigating the shift from in-person to virtual care—a shift that was also challenging for some patients. These changes had implications for the present study. For instance, we did not design the study to systematically evaluate potential differences in TranS-C delivery (i.e., in-person versus virtual versus phone). As another example, there was substantial turnover in providers and patients, leading to more discontinuity across treatment than anticipated. Sixth, some design choices were made to respect the expertise and preferences of our CMHC partners. For example, providers had the option to deliver TranS-C in a group or individual format. Even though this introduced variance into the study, it has been critical to the CMHCs, providers, and patients that we balance rigor with flexibility. We deliberated about whether to control for these variations necessitated by COVID-19 and the CMHC contexts. Ultimately, we decided against a prespecifying a comprehensive list of possible covariates, given the statistical drawbacks of controlling for many variables (e.g., [94-97]). At the conclusion of the trial, the sources of variation that resulted from the COVID-19 pandemic and needs/preferences of our community partners will be carefully considered as to whether they should be included as covariates.

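### The Aim 2 model leaves out the mid-treatment provider ratings collected in both arms, which exposes the Adapted versus Standard contrast to bias if provider loss differs by arm; for Aim 1 the mid score belongs only in a sensitivity analysis.

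*Combined protocol and SAP*

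**What the plan says.** - **Model occasions.** Aim 1 (Section 4.3): "The level 1 equation will include dummy-coded time indicators as the predictor (0 = pretreatment, 1 = post-treatment"). Aim 2 (Section 4.4) has the same two codes, "0 = pre-treatment, 1 = post-treatment". Neither coding has a value for a mid-treatment record.
- **Provider data.** Section 3.6.1: "Provider assessments are completed after TranS-C training, at mid-treatment, and at post-treatment". Table 1 shows all three fit ratings at each of these occasions, and the schedule is the same for Adapted and Standard.
- **Patient data.** Section 3.6.2 says that assessments in immediate TranS-C "are completed at pre-treatment, mid-treatment, post-treatment, and six months after treatment (6FU"). UC-DT patients are assessed at pre-treatment and again at the end of the delay, with nothing between. Table 1 gives mid-treatment scores for PROMIS-SD, PROMIS-SRI and the Sleep Health Composite, but none for SDS or the DSM-5 Cross-Cutting Measure.
- **Missing data.** Section 4.1: "Analyses will use all available data (intent-to-treat"), and "If dropout is related to other variables, they will be included as predictors".
- **Use of mid scores.** In the effect analyses they appear only in the second sensitivity set of Section 4.6. Patients without a later assessment who "had achieved meaningful clinical improvement by mid-treatment" have their mid score used as the post score.
- **Attrition.** Section 3.8 allows 20%. Section 5 reports that "there was substantial turnover in providers and patients".

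**The concern.** A provider who rates TranS-C at mid-treatment and is then lost contributes only the post-training rating to the Aim 2 model. A likelihood analysis of two occasions is valid if loss depends only on that first rating and the covariates. If providers with a poor mid-treatment opinion are more likely to be lost, the estimated post mean in their arm is too high. The mid rating that would account for this has been collected and is not used.

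The two courses differ in burden (eight 50-minute sessions against four 20-minute sessions, Sections 3.4.1 and 3.4.2), so unequal loss is plausible. Acceptability is the primary provider outcome, and the condition-by-time effect on it is the Aim 2 test.

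The same omission occurs in Aim 1 for PROMIS-SD and PROMIS-SRI, but there the mid score exists in one arm only, and that changes the remedy.

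**Working it through.** **1. The plan's own figures.** Section 3.8 takes d = 0.80, 8 clusters of 10 providers and an ICC of 0.01.
- Design effect: 1 + (10 − 1) × 0.01 = 1.09.
- Effective number per arm: 40 / 1.09 = 36.7.
- Normal approximation: 0.80 × √(36.7 / 2) = 3.43, and 3.43 − 1.96 = 1.47, so power is 0.929. With a t reference on 8 − 2 = 6 df it is 0.813. Both agree with the stated figure of over 80%.
- Attrition: 80 × 1.2 = 96 providers, as stated.

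**2. Set-up for Aim 2.** From the documents: d = 0.80 and a 20% overall allowance. Assumed, because the documents give no values:
- unit SD, with correlations first–mid 0.5, first–post 0.4 and mid–post 0.7;
- an Adapted advantage of 0.5 SD at mid and 0.8 SD at post;
- loss after mid-treatment, with the odds of loss doubling per SD lower mid rating.

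Estimators within each arm, with coefficients fitted in those who have a post rating and means taken over everyone in the arm:
- Two occasions: post mean = b0 + b1 × mean(first).
- Three occasions: post mean = b0 + b1 × mean(first) + b2 × mean(mid).

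These match the likelihood estimates under an unstructured covariance when the only missing value is the post rating.

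**3. Aim 2 results (large-sample simulation, true d = 0.80).**

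| Loss, Standard / Adapted | Odds ratio per SD | Two occasions | Three occasions |
|---|---|---|---|
| 20% / 20% | 2 | 0.80 | 0.80 |
| 30% / 10% | 2 | 0.74 | 0.80 |
| 30% / 10% | 2.7 | 0.71 | 0.80 |
| 20% / 20%, rating-related in Standard only | 2.7 | 0.71 | 0.80 |

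The shift at odds ratio 2 is 0.80 − 0.74 = 0.06 SD. With the loss rates swapped the sign reverses: 0.80 + 0.06 = 0.86. Put into the power formula of step 1, 0.74 × √(36.7 / 2) = 3.17, and 3.17 − 1.96 = 1.21, which gives 0.887 against 0.929.

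**4. Aim 1, PROMIS-SD.** All values are assumed: SD 6, the same correlations, a true contrast of −5.0 (UC-DT change 0, TranS-C change −3 at mid and −5 at post), and an odds ratio of 2 per SD of pre-to-mid change. In each pair, the first figure is for non-improvers leaving and the second for improvers leaving.

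| Loss, TranS-C / UC-DT | Planned two-point | Mid score added in TranS-C only |
|---|---|---|
| 20%, response-related in TranS-C only | −5.4 / −4.6 | −5.0 / −5.0 |
| 30%, response-related in TranS-C only | −5.6 / −4.4 | −5.0 / −5.0 |
| 20% / 20%, response-related in both | −5.0 / −5.0 | −4.6 / −5.4 |
| 30% / 30%, response-related in both | −5.0 / −5.0 | −4.4 / −5.6 |
| 20% / 10%, response-related in both | −5.2 / −4.8 | −4.8 / −5.2 |

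Correcting one arm removes the bias when the mechanism is confined to TranS-C. It creates bias of the same size when the mechanism and rate are the same in both arms. At 20% against 10% it gains nothing.

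**5. The planned substitution for improvers.** With an assumed improvement threshold of 1 SD, a true d of 0.50 and no response-related loss in UC-DT, this analysis gives 0.51 to 0.62 at 20% loss and up to 0.75 at 40%, across odds ratios of 1.6 to 4.5. In these runs it never falls below the truth, because only favourable mid scores are brought in.

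**The case against.** **Both primary effects are biased.** A reader might infer this, but the documents do not support it. A condition-by-time effect is a difference between arms. When rate and mechanism of loss are the same in both, the errors cancel, as the first row for Aim 2 shows. The plan gives no loss rates by arm.

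**The two-point coding breaks the all-available-data promise.** This also goes too far. Section 4.1 pairs the promise with intent-to-treat and, in the same paragraph, defines the comparisons as change from pre- to post-treatment. That fixes the contrast. It neither requires nor forbids letting mid records inform it.

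**The plan itself suspects that leavers are selected on response.** Section 4.6 raises this for patients only, as a check on whether any non-completers had improved. Its remark on early responders belongs to the dose analyses. Section 5 reports provider turnover as a consequence of the pandemic and does not tie it to ratings.

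**Safeguards exist.** Section 4.2 reports dropout by stage, Section 4.1 adds predictors of dropout, and Section 4.6 uses some mid scores. These count, but they do not close the gap. A mid score is measured after randomisation, so adjusting for it as a predictor would remove part of the effect. Section 4.2 is descriptive, and the substitution in Section 4.6 is one-sided.

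**The size is modest and assumed.** This stands. In the Aim 1 setting with 240 per arm and 20% loss, the standard error is 0.109 without the mid score and 0.108 with it, so the gain is in bias and not in precision.

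**The absent UC-DT mid visit justifies a symmetric Aim 1 model.** This stands too, and it decides the Aim 1 recommendation.

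**Conclusion.** For Aim 2 the point holds. The model omits ratings that are collected in both arms, and the omission matters when provider loss after mid-treatment differs between Adapted and Standard in rate or mechanism. The illustrated shift is about 0.06 SD on a true 0.80 at 30% against 10% loss, and zero at equal loss. The omission is certain from the text; its size rests on assumed correlations and dropout strength. Providers lost before mid-treatment are not helped.

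For Aim 1 it would be tempting to conclude that the primary model should be rebuilt around the mid score. The assessment schedule does not support that, because the score exists only in immediate TranS-C before the comparison point, and a one-arm correction can add as much bias as it removes. A sensitivity analysis is the proper place. The point does not reach SDS or the DSM-5 Cross-Cutting Measure.

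**What to change.** **Aim 2 (Section 4.4).** Code time with three levels (post-training, mid-treatment, post-treatment), with condition by time at each and an unstructured within-provider covariance. Keep the post-treatment contrast as primary. In the same edit, reconcile the label of time 0, which Section 4.4 calls pre-treatment although Section 3.6.1 and Table 1 place the first rating after training.

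**Aim 1 (Sections 4.3 and 4.6).** Keep the two-point model as primary. Add a sensitivity analysis for PROMIS-SD and PROMIS-SRI that uses the mid score for every immediate TranS-C patient with a missing post score, whether improved or not. The score can enter as an extra occasion in the outcome vector or through multiple imputation within arm. State that this removes bias only if response-related leaving is mainly in TranS-C, and can add bias if it also occurs in UC-DT. Report loss by arm beside it.

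**Cost.** SAP wording and a slightly larger model: the 3 × 3 provider covariance has 3 variances and 3 covariances, so 6 parameters. No new data are needed. Section 6 has assessments continuing to August 2023, so at this version the change could still be specified before the final analysis.

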## 2 AIMS

Together, the goal of the present hybrid type 2 effectiveness-implementation study [48, 49] is to evaluate the implementation and effectiveness outcomes of TranS-C in CMHCs of counties across California in the United States. The study will be conducted in three phases. This protocol will focus on Phase 1, the Implementation Phase, during which TranS-C is implemented in CMHCs via facilitation (see Method). Phase 2 is the Train-the-Trainer Phase, during which CMHC providers learn to train and supervise their peers in the delivery of TranS-C. Phase 3 is the Sustainment Phase, during which we will assess the extent to which TranS-C activities are sustained after facilitation has ceased.

During the Implementation Phase, sites are cluster-randomized by county to Adapted TranS-C or Standard TranS-C with 1:1 allocation. Then, within each county, patients are randomized to immediate TranS-C or UC-DT. The first aim is to assess the effectiveness of TranS-C, compared to UC-DT. We hypothesize that, compared to UC-DT, TranS-C (combined Adapted and Standard) will be associated with larger reductions in the primary patient outcome of sleep disturbance and the secondary patient outcomes of sleep-related impairment, functional impairment, and psychiatric symptoms. We also hypothesize that TranS-C's benefits for functional impairment and psychiatric symptoms will be mediated by improvements in sleep and circadian problems. The second aim is to evaluate whether TranS-C treatment condition (Adapted versus Standard TranS-C) is associated with fit to the CMHC context, operationalized as provider ratings of acceptability, appropriateness, and feasibility. We hypothesize that

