### 3.5.2.2 Secondary Outcomes

*Sleep-Related Impairment.* The 16-item PROMIS-Sleep Related Impairment (PROMIS-SRI) assesses daytime impairment related to sleep problems over the past seven days on a scale from 1 (not at all/never) to 5 (very much/always) [62]. Scores range from 16-80, with higher scores indicating greater impairment (e.g., daytime sleepiness, difficulty concentrating). This measure has demonstrated excellent psychometric properties [61, 62].

*Functional Impairment.* Functional impairment is assessed via the Sheehan Disability Scale (SDS) [76]. Impairment in work and school, social life, and home and family is rated on a scale from 0 (not at all) to 10 (extremely). Scores range from 0-30, with higher scores indicating greater impairment. This measure has demonstrated good reliability and validity [76, 77].

*Overall Sleep Health.* The Sleep Health Composite is proposed to capture overall sleep health for the complexity of sleep problems in SMI that are covered by TranS-C [78]. It is defined as the sum of scores on six sleep health dimensions (each dimension dichotomized as 1 = good; 0 = poor): Regularity (midpoint fluctuation), Timing (mean midpoint), Efficiency (sleep efficiency), Duration (total sleep time), Satisfaction (sleep quality question on PROMIS-SD), and Alertness (daytime sleepiness question on PROMIS-SRI). All dimensions – except Satisfaction and Alertness – are assessed via questions about sleep-wake patterns over the past seven days (e.g., *In the past week, what time have you usually woken up in the morning?*). Scores range from 0-6, with higher scores indicating better sleep health. Initial validity of this measure has been established [78].

*Psychiatric Symptoms.* The DSM-5 Cross-Cutting Measure assesses psychiatric symptoms across 13 mental health domains. Participants rate how often they were bothered by each symptom on a scale from 0 (not at all) to 4 (nearly every day). Scores range from 0-52, with higher scores indicating more severe symptoms. This measure has demonstrated good test-retest reliability and clinical utility [79, 80].

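### Aim 1's indirect-effect test measures change in sleep and change in function or symptoms over the same interval, so a significant result cannot show that sleep produced the benefit

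*Combined protocol and SAP*

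**What the plan says.** Section 2 hypothesizes that "TranS-C's benefits for functional impairment and psychiatric symptoms will be mediated by improvements in sleep and circadian problems". Section 4.3 turns this into one sentence: the indirect effects of TranS-C relative to UC-DT "through improvements in sleep disturbance and sleep-related impairment will be tested using multilevel structural equation modeling". It names no mediator visit, lag, reverse model or confounding analysis.

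Three other places fix which data can be used:

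- Section 4.1: "Analyses comparing TranS-C to UC-DT will evaluate change in outcomes from pre-treatment to post-treatment". The time indicator in section 4.3 agrees ("0 = pretreatment, 1 = post-treatment").
- Section 3.6.2: assessments in the UC-DT "condition are completed at pre-treatment and four or eight weeks after pre-treatment". TranS-C then begins, and the remaining visits follow it.
- Table 1: PROMIS-SD and PROMIS-SRI are scheduled at mid-treatment. The Sheehan Disability Scale (SDS) and the DSM-5 Cross-Cutting Measure are not.

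On content, section 3.5.2.2 says that PROMIS-SRI "assesses daytime impairment related to sleep problems over the past seven days". It describes SDS as rating impairment at work or school, in social life and at home. Section 2 lists both among the secondary patient outcomes of this aim.

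**The concern.** Randomization identifies the effect of treatment on sleep and its effect on function. It does not identify the path from sleep to function. That path needs either temporal order or an argument that nothing else links the two changes, and the plan offers neither.

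The alternatives are realistic here. Section 3.7 states that patients know whether they are in the immediate or the delayed arm, and the mediators and outcomes are all patient ratings, so a general response to being treated could move every score together. For the PROMIS-SRI to SDS path, overlapping content is a further route to correlation.

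The abstract presents sleep and circadian problems as a probable mechanism of serious mental illness, so a positive indirect effect is likely to be read as support for that mechanism. The limitations in section 5 mention neither temporal order nor content overlap.

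**Working it through.** **1. The plan's own figure.** Section 3.8 gives d = 0.89, two-sided alpha 0.05 and 240 patients per arm before the attrition allowance. Power = Φ(d√(n/2) − 1.96).

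- n = 240 per arm: 0.89 × √120 = 9.75, power above 0.999.
- n = 30 per arm (one reading of that section's 60 patients): 0.89 × √15 = 3.447, Φ(1.487) = 0.931.

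The claim of over 90% reproduces either way. It concerns the treatment difference; the documents give no figure for the indirect effect.

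**2. Which values can enter the randomized contrast** (Table 1 and section 3.6.2):

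| Visit | PROMIS-SD, PROMIS-SRI | SDS, DSM-5 | UC-DT before TranS-C |
|---|---|---|---|
| Pre | yes | yes | yes |
| Mid | yes | no | no visit |
| Post | yes | yes | yes (post-delay) |
| 6 months | yes | yes | no; follows delayed TranS-C |

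Only pre and post remain. Table 1's note lets baseline PROMIS-SD come from screening within the previous month. That moves the mediator's starting point but does not place its change before the outcome's.

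**3. Illustrations with no effect of sleep on symptoms.** T is treatment, M the change in sleep and Y the change in function or symptoms. Within-arm variances are 1 and N = 480. Path a is T to M, b is M to Y given T, and c is the total effect of T on Y. Significance means that both a and b exceed 1.96 standard errors, with z_b = r√480/√(1 − r²). This simple model stands in for the multilevel SEM and omits covariates and county terms. Only d = 0.89 comes from the plan; the other effect sizes and all correlations are assumptions.

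*A. Treatment acts on both, and symptoms feed back to sleep.* Y = 0.50T + e; M = (0.89 − 0.50r)T + rY + u. Then a = 0.89, b = r, c = 0.50, and z_a = 9.75.

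| r | indirect = 0.89r | apparent share | z_b |
|---|---|---|---|
| 0.2 | 0.178 | 36% | 4.47 |
| 0.3 | 0.267 | 53% | 6.89 |
| 0.4 | 0.356 | 71% | 9.56 |

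The smallest z gives Φ(4.47 − 1.96) = 0.994, so at least 99% of trials are significant.

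*B. Treatment reaches sleep only through function.* Y = dT + e; M = rY + √(1 − r²)u. Then a = rd, b = r, c = d, and the apparent share is r² (9% to 49%). Path b is nearly always significant (z_b at least 6.89), so z_a = rd√120 decides.

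*C. One common response moves both.* U = dT + e, with M and Y each loading √r on U. Then z_a = √r·d√120 and the apparent share is r (30% to 70%).

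| d | B, r = 0.3 to 0.7 | C, r = 0.3 to 0.7 |
|---|---|---|
| 0.89 | 83% to 100% | 100% |
| 0.5 | 38% to 97% | 85% to 100% |
| 0.3 | 17% to 63% | 44% to 79% |

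Simulation agrees with these rates to within about three percentage points. Under true forward mediation, simulation gives about 89% to 100%, so a positive result separates the explanations poorly at the plan's effect size.

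**4. Would a lag to six months settle it?** Consider regressing six-month function on pre-to-post sleep change, adjusted for post-treatment function.

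- If true mediation is complete by post-treatment and function is then carried forward, the sleep coefficient is zero and is significant in about 5% of runs.
- If one factor loads 0.5 on all three scores and sleep has no effect, all pairwise correlations are 0.25. The coefficient is (0.25 − 0.0625)/(1 − 0.0625) = 0.20, with residual variance 0.90. Then z = 0.20/√(0.90/(0.9375n)) = 3.16 at n = 240 and 4.47 at n = 480, significant in about 88% and 99%.

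So the lag can miss true mediation and can support false mediation.

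**The case against.** The most direct rebuttal is that Table 1 has mid-treatment sleep scores, which would place the mediator before the outcome. It fails: UC-DT has no mid-delay visit, and SDS and DSM-5 are not collected at mid-treatment.

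Other objections stand and limit the point. This is one supplementary sentence about secondary outcomes. The primary comparison is unaffected, and the short control schedule is a disclosed compromise (sections 3.6.2 and 5). Section 4.3 names no mediator visit, so the shared interval is inferred from sections 3.6.2 and 4.1 and Table 1. The plan speaks of mediation and indirect effects, and it sets no rule for declaring sleep the driver.

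A reader might go further in three ways that the documents do not support:

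- *That a significant indirect effect is close to guaranteed.* It is in illustration A. In B it falls to 17–63% at d = 0.3.
- *That the data cannot contradict the hypothesis.* They can: no treatment effect on sleep, or no association between sleep and outcome given treatment, would fail the test.
- *That PROMIS-SRI is not a sleep measure and must be dropped.* Section 3.5.2.2 uses its sleepiness item as the Alertness dimension of the Sleep Health Composite, and daytime impairment is a core treatment target (sections 3.4.1 and 3.4.2). The overlap concerns the path to SDS, not to DSM-5, and the documents give no correlation by which to size it.

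**Conclusion.** The concern holds in a limited form. The planned test can yield a result consistent with mediation. It cannot show that sleep changed first or caused the benefit, because the randomized contrast offers a single shared interval. That conclusion follows from the visit schedule and needs no assumed figures.

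The size does rest on assumptions. An apparent share of 36% to 71% with a true share of zero depends on the assumed 0.50 SD symptom effect and correlations of 0.2 to 0.4. The false-positive rates in B and C depend on the assumed range of r and on which effect size is realized. They are illustrations of what the test tolerates, not forecasts for this trial. What is affected is the interpretation of the mechanistic claim; the Aim 1 treatment effects themselves are not in doubt on this account.

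**What to change.** In section 4.3:

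1. State that the TranS-C versus UC-DT indirect effect will be reported as a concurrent association consistent with mediation, and not as evidence that sleep change caused the benefit.
2. Make PROMIS-SD the main mediator. Report PROMIS-SRI separately as secondary, noting its content overlap with SDS.
3. Add a reverse-path model (SDS or DSM-5 change as mediator, PROMIS-SD as outcome) and a sensitivity analysis for unmeasured mediator-outcome confounding.
4. If lagged models from post-treatment to six months are run in TranS-C recipients, label them exploratory and make them symmetric, each direction adjusted for the post-treatment value of its own outcome. For the reasons in step 4 of the working, and because they have no untreated comparison, they should not be a rule for concluding that sleep drives the benefit.

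Add a sentence on temporal order to the limitations in section 5.

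The cost is a weaker mechanistic claim and a little extra analysis of data already scheduled. Recruitment closed in August 2022 (section 6), so a visit during the delay can no longer be added for most UC-DT patients; the remedy has to lie in analysis and reporting.
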